# 6.1.3. Product Storage and Stability

Vaginal applicators containing active test article or placebo will be stored at room temperature (15-30°C.) with transient spikes up to 40°C permitted if they last less than 24 hours.

# 6.2. Dosage, Preparation and Administration of Study Intervention/Investigational Product

## **Preparation**

No formal preparation is required for the study product. The unmasked Research Pharmacist or designated unmasked study personnel maintaining the study product accountability will select the appropriate kit based on the randomization scheme and will label the kit with the subject's name, subject ID number, treatment number, and any other hospital required identifying information.

#### Administration

Study personnel will provide both verbal and written instructions for proper storage and administration. The first dose will be administered by the subject while the subject is still in clinic. The remaining 5 doses will be administered twice daily (morning and evening) with at least 8 hours between doses by the subject at home. If the subject received her first dose after 3 pm, she will be instructed to administer the next dose the following morning.

## Dose of Study Agents/Interventions

Active test article will be composed of 5 mL of 5% Monolaurin Vaginal Gel prepared as pre-filled vaginal gel applicators of identical likeness to placebo. Vehicle Placebo Gel will contain 5 mL of the vehicle used in the active test article.

# 6.3. Modification of Study Intervention/Investigational Product for a Participant

If a subject is found to have a positive test for HIV, chlamydia or gonorrhea or Grade 3 laboratory abnormality from Visit 1, she will be notified of the results, withdrawn from receiving further study product, but will be followed for safety and efficacy. All subjects who have received even a single dose of study drug will be followed for safety and efficacy.

If any subject experiences a severe AE related to the study product, further doses will be discontinued.

If the subject misses a dose, she should note the missed dose on the memory aid, save the unused applicator, and resume dosing at the next recommended scheduled dose.

# 6.4. Accountability Procedures for the Study Intervention/Investigational Product(s)

The unmasked Research Pharmacist will be responsible for maintaining complete records and documentation of study product receipt, accountability, dispensation, storage conditions, and final disposition of the study product. All study products, whether administered or not, must be documented on the appropriate study product accountability record or dispensing log.

Study personnel will document on the CRF the time of the application of the first study dose. The first dose applicator may be discarded. Subjects will be instructed to return the kit (containing used and/or unused vaginal applicators) to study personnel at the clinic for Visit 2. The used kit and applicators will be placed in a sealed plastic bag for transport to the study site. Once the study personnel have verified the test article accountability, the kits and used applicators may be discarded in an appropriate medical waste container.

Upon completion or termination of the study and after the final monitoring visit, any remaining unused study product will either be returned or destroyed appropriately at the clinical site as per Sponsor requirements and instructions.

# 6.5. Assessment of Subject Compliance with Study Intervention/Investigational Product

Study personnel will count the number of used/unused applicators contained in each returned subject kit and record this information in the test article accountability section of the subject's CRF.

## **6.6.** Concomitant Medications/Treatments

Administration of any medications, therapies, or vaccines will be documented in the subject's source documentation and reported on the subject's data acquisition screen. Concomitant medications will include all medications, vitamins, and supplements taken within the 30 days before enrollment and through Visit 3 (Day 28) or early termination, whichever occurs first.

Each subject will be instructed to not use any systemic, vaginal, or perineal antibiotic, antifungal, immunosuppressant, or anti-inflammatory medication except oral nonsteroidal anti-inflammatory medication during study participation from study Day 1 through Visit 3 unless absolutely necessary.

Treatment with any prescription medication(s), over-the-counter preparations and non-prescription medication(s) intended to treat the subject for vaginosis will be used only if subject is considered a clinical failure. In this case, she will be referred to her provider for standard of care treatment. All treatment medications must be documented on the concomitant medications CRF.

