
Visit 2 (Day 8 [Window Days 8-15]): At this visit, the study team will review the memory aid, the intercurrent medical history with assessment of AEs and SAEs, changes to the concomitant medications, a gynecological exam and a targeted physical exam based on symptoms will be performed, and vaginal pH and vaginal swabs for Gram stain, saline wet mount, KOH 10% wet mount and culture will be obtained. If signs and symptoms of vaginitis fail to resolve, the study clinician will refer the subjects to their clinician for standard treatment for BV or other etiologies of vaginitis at the clinician's discretion and the subject will be classified as a clinical failure at Visit 2 and/or 3. Follow-up hematology and chemistry labs (WBC count, hemoglobin, platelets, neutrophil count, creatinine, AST, ALT, total bilirubin, random glucose) for safety evaluation will be performed.

Visit 3 (Day 28 [Window Days 22-31]) will include a review of the intercurrent medical history, concomitant medications, AEs and SAEs, and a gynecological exam and a targeted physical exam based on symptoms. Vaginal pH and vaginal swabs for Gram stain, saline wet mount, KOH 10% wet mount and culture will be performed.

Subjects who have positive HIV, *Chlamydia*, or *Neisseria gonorrhoeae*, or a grade 3 laboratory results from Visit 1 will be contacted within 24 hours of receipt of laboratory results and will be asked to follow up with their provider. These subjects will be asked to discontinue the study therapy if the test result returns during the study product administration period of the study.

These subjects will continue in efficacy and safety follow up.

At visits 1, 2 and 3, an extra vaginal swab will be collected for future use, if subject consents to future use of specimens.

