- Subjects will be counseled to come in for an unscheduled visit if their vaginitis symptoms recur/worsen between Visit 2 and 3.
- Document Investigator assessment of clinical cure.

If the signs and symptoms of BV fail to resolve and further treatment is required (in the Investigator's opinion), the subject will be referred to her provider for standard treatment. Therapy will be recorded on the appropriate source document and electronic CRF (eCRF) pages and the subject will be followed through Visit 3 for safety. At Visit 3, these subjects will be classified as a clinical failure.

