# 11.3. Study Objectives and Endpoints

The primary study objectives are to compare 5% Monolaurin Vaginal Gel with vehicle placebogel (excipients only) with respect to 1) safety and tolerability, and 2) efficacy by clinical cure at Visit 2. The primary safety outcome measures are the number of subjects reporting solicited urogenital AEs following the first dose of the study product through Visit 2 (Days 8-15) and the number of

Failure

Not Evaluable

subjects reporting SAEs considered product related following the first dose of study product through Visit 3 (Day 22-31). The primary efficacy outcome measure is the proportion of subjects with clinical cure in each study arm at Visit 2 (Days 8-15).

A clinical cure is defined by normal Amsel criteria. Normal Amsel criteria are defined as: normal physiological vaginal discharge, whiff test negative for any amine "fishy" odor, saline wet mount less than 20% for clue cells, and vaginal pH is <=4.5.

A clinical failure is defined by a) one or more abnormal Amsel criteria, b) early discontinuation of study therapy due to lack of treatment effect, c) use of any vaginosis therapy other than study product during the study, or d) in the investigators opinion, requires additional treatment for vaginosis.

Subjects who do not meet the criteria for either the clinical cure or clinical failure definitions are not evaluable for clinical cure.

A secondary efficacy outcome measure is the proportion of subjects with therapeutic cure in each study arm at Visit 2 (Day 8-15) and at Visit 3 (Day 22-31). Therapeutic cure is defined as both a clinical cure AND a bacteriological cure (Nugent score 0-3). Subjects who were clinical failures, or have a Nugent score >3 are therapeutic failures. Subjects who are not evaluable for clinical cure, or do not have a Nugent score result are not evaluable for therapeutic cure.

If the clinical cure outcome is	and the Nugent (bacteriological) score result is	then the overall therapeutic cure outcome is
Cure	0-3	Cure
Cure	>3	Failure
Cure	Not Evaluable	Not Evaluable
Failure	0-3	Failure
Failure	>3	Failure
Failure	Not Evaluable	Failure
Not Evaluable	0-3	Not Evaluable

 Table 3:
 Bacterial Vaginosis: Determination of Therapeutic Cure

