3.3.3. Clinical Cure

A clinical cure is defined by normal Amsel criteria. Normal Amsel criteria are defined as: normal physiological vaginal discharge, whiff test negative for any amine "fishy" odor, saline wet mount

less than 20% for clue cells, and vaginal pH is <=4.5. All four criteria must be normal and none of the clinical failure criteria listed below can be met to be considered a clinical cure.

A clinical failure is defined by at least one of the following:

- a. one or more abnormal Amsel criteria,
- b. early discontinuation of study therapy due to lack of treatment effect,
- c. use of any vaginosis therapy or systemic antimicrobial therapy other than study product during the study, or
- d. in the investigator's opinion, requires additional treatment for vaginosis.

Subjects who do not have enough information to determine a clinical cure or clinical failure status will not be evaluable for clinical cure.

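### Protocol Sections 4, 6.6 and 7.2 word rescue referral differently, and SAP 3.3.3 omits Section 7.2's Visit 3 failure rule, so a woman can be a Visit 3 failure under the protocol and a cure under the SAP

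*Protocol*

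**What the plan says.** Three places in the protocol deal with a woman who still needs treatment at Visit 2.

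- Section 4, under Visit 2: "If signs and symptoms of vaginitis fail to resolve, the study clinician will refer the subjects to their clinician for standard treatment for BV" or for another cause of vaginitis. The consequence is that "the subject will be classified as a clinical failure at Visit 2 and/or 3".
- Section 6.6, on concomitant treatment: other vaginosis treatment may be used "only if subject is considered a clinical failure. In this case, she will be referred to her provider for standard of care treatment". It states no consequence for Visit 3.
- Section 7.2, the Visit 2 instructions: "If the signs and symptoms of BV fail to resolve and further treatment is required (in the Investigator's opinion), the subject will be referred". The consequence is explicit: "At Visit 3, these subjects will be classified as a clinical failure".

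Protocol 11.3 defines failure by (a) any abnormal Amsel item, (b) stopping early for lack of effect, (c) other vaginosis therapy, or (d) the investigator's opinion that more treatment is needed. SAP 3.3.3 repeats this list, widens (c) to systemic antimicrobials, and gives (d) as "in the investigator's opinion, requires additional treatment for vaginosis". A cure needs all four Amsel items normal and none of (a) to (d) met. Neither definition mentions referral. SAP 3.3.4 says that cure outcomes are assessed at Visits 2 and 3, and SAP Listing 24 shows the failure reasons, including need for further treatment, on a separate row for each visit.

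**The concern.** The three conditions need not select the same women. Section 4 turns on vaginitis of any cause, Section 6.6 on failure status, and Section 7.2 on unresolved BV together with the investigator's judgement. Sites have no single text to follow.

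The larger problem is the endpoint. Section 7.2 carries a Visit 2 referral forward to a Visit 3 failure. The SAP, which will be programmed, has no such sentence. SAP Section 12 declares that its use of last observation carried forward departs from protocol 11.3, but it does not declare this difference. Clinical and therapeutic cure at Visit 3 are named secondary outcomes, so a programmer would have to decide how to classify these women.

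**Working it through.** No figure in the plan is in dispute, so the check is a comparison of texts followed by a statement of scale.

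**Step 1: do the conditions differ?** Protocol 5.1 admits women with asymptomatic BV, and protocol 11.3 says "A clinical failure is defined by a) one or more abnormal Amsel criteria". Take a woman without symptoms whose only abnormal Visit 2 finding is pH above 4.5. She is a clinical failure. If Section 6.6 is a trigger, she is referred. If it is a limit, she may be treated but need not be referred. Section 4 would not refer her on symptoms. Section 7.2 refers her only if the investigator judges that treatment is required.

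**Step 2: do the Visit 3 consequences differ?** Take women referred at Visit 2 under Section 7.2.

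| Course after referral | Protocol 7.2 | SAP |
|---|---|---|
| Takes vaginosis therapy | Failure | Failure under (c) |
| Cure status cannot be determined at Visit 3 | Failure | Failure in mITT, ITT and Evaluable: SAP 6.5 carries the Visit 2 status forward |
| Returns, an Amsel item abnormal | Failure | Failure under (a) |
| Returns, no therapy, all Amsel items normal, (d) not recorded at Visit 3 | Failure | Failure if the Visit 2 (d) persists; cure if (d) is judged afresh at each visit |

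Only the last row is in conflict. The requirement in SAP 3.3.3 that no failure criterion be met carries no visit label, which favours persistence. The visit-level assessment in SAP 3.3.4 and the visit rows of Listing 24 favour a fresh judgement. The SAP does not choose.

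**Step 3: scale.** Let k_g and k_v be the numbers of last-row women in the gel and vehicle arms. Neither can be obtained from the documents, and either may be zero. With the planned mITT sizes of 60 and 30 (SAP Section 5), the fresh-judgement reading exceeds the 7.2 reading as follows:

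- gel clinical cure rate: k_g/60, so 1/60 = 1.7 points per woman;
- vehicle clinical cure rate: k_v/30, so 1/30 = 3.3 points per woman;
- gel minus vehicle difference: k_g/60 − k_v/30.

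The difference moves only if the affected share differs between arms. With k_g = 2 and k_v = 1, for example, 2/60 − 1/30 = 0. Therapeutic cure also needs a Nugent score of 0 to 3, so no more women can be affected there than for clinical cure.

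**The case against.** Several points on the other side stand.

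- Section 6.6 can be read as a limit. Its opening makes failure a necessary condition for rescue, and the referral sentence may only say who provides the treatment. On that reading it does not refer every failure, although its wording that she will be referred leaves doubt.
- The SAP does not ignore the matter. Criterion (d) is the judgement on which Section 7.2 refers, and criterion (c) already fails treated women. The gap is whether (d) persists.
- The primary endpoint is little affected. Any abnormal Amsel item at Visit 2 is already a failure, and so is (d).
- Protocol 11.4 plans three formal tests, none at Visit 3, and SAP 8.2 gives estimates and intervals only.
- Randomisation is stratified by site and assessors are masked, so site habit alone should not favour an arm.

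A reader might go further and infer that the choice between Sections 6.6 and 7.2 shifts the Visit 3 arm difference by several points. Assume Visit 2 failure of 50% (gel) and 80% (vehicle), 30% of failures left unreferred under 7.2, and half of those normal by Visit 3. Then 0.50 × 0.30 × 0.50 = 7.5 points, 0.80 × 0.30 × 0.50 = 12 points, and the shift is 4.5 points. With 10% to 50% unreferred, 0.30 × 0.10 × 0.50 to 0.30 × 0.50 × 0.50 gives 1.5 to 7.5 points. The documents do not support this. Every input is assumed, and the calculation attaches 7.2's automatic failure to referral under 6.6, which states no Visit 3 consequence. With equal Visit 2 failure in the two arms the same formula gives no shift.

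**Conclusion.** The point holds in a limited form. The three protocol sections word the referral condition differently and disagree on, or omit, its Visit 3 consequence. The SAP neither carries Section 7.2's rule nor declares a departure from it. The conflict concerns women referred at Visit 2 who take no therapy, return with normal Amsel items and are not again judged to need treatment. It bears on secondary Visit 3 rates that are estimated without tests.

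Its size is unknown. The per-woman figures of 1.7 and 3.3 points assume the planned arm sizes and say nothing about how many such women there are. If the affected share were larger in the vehicle arm, the fresh-judgement reading would give a smaller gel advantage than 7.2. If the shares were equal, only the rates would move. The documents do not support a claim that Visit 3 cure mainly reflects referral habit, or that the primary result is at risk.

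**What to change.** 1. Reconcile protocol Sections 4, 6.6 and 7.2 to one referral condition and one stated Visit 3 consequence. Which condition is right is a clinical decision for the sponsor. SAP 6.6 shows enrolment well advanced, so this helps only women yet to reach Visit 2.
2. In protocol 11.3 and SAP 3.3.3, state that a woman who meets criterion (d) and is referred at Visit 2 is a clinical and therapeutic failure at Visit 3, as protocol 7.2 already says. If the sponsor prefers to judge (d) afresh at Visit 3, declare that departure from 7.2 in SAP Section 12. Either can be settled before database lock.
3. Programme the rule from the Visit 2 entry for need of further vaginosis treatment. Listing 24 shows it by visit and notes that it comes from the eCRF, so a new field is largely redundant. If the reconciled condition allows referral without that opinion, the text must also say how those women are classified.

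The cost is a protocol clarification and one or two SAP sentences. The downside of carrying the failure forward is that Visit 3 cure rates may be somewhat lower, by an amount the documents do not allow to be estimated.

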#### 7. STUDY SCHEDULE

# 7.1. Screening and Enrollment (Visit 1, Day 1)

Subjects should be scheduled for visits when they are not menstruating and instructed to avoid inserting any substance into the genital tract for 48 hours before examination at Visit 1, when possible. Subjects may present after having clinical evaluation by a non-study clinician or may present to the research clinic directly.

The following procedures will be performed:

- Obtain signed informed consent. This should be performed prior to conducting any of the assessments listed below.
- Review inclusion/exclusion criteria and collect demographic information.
- Obtain medical history and concomitant medications (prescription and over-the-counter drugs, supplements, and vitamins taken 30 days prior to enrollment will be reviewed and documented).
- Review of contraceptive methods and recent menstrual history.
- Review sexual history.
- Review subject report of history of previous episodes of BV and if noted, the number of episodes of BV in the previous 12 months and treatments given.
- Assessment of current symptoms of BV
- Perform physical exam.
- Perform urine pregnancy test for female subject of childbearing potential prior to pelvic exam. Must be negative prior to receipt of study drug.
- Gynecologic exam for evaluation of the cervix, vagina, and vulva:
  - Assessment for genital tract infections and lesions. If evidence of active lesions
    consistent with herpes simplex virus infection or other sexually transmitted
    infection (e.g., syphilis), subject will be excluded and may be referred to her
    provider for further management.
  - Document vaginal discharge (quantity, color, odor, and consistency).
  - Document objective signs of inflammation (edema, erythema, excoriation). Inspection and appearance of the cervix, vagina, and vulva, and document presence or absence of objective signs of inflammation (edema, erythema, excoriation).
  - Document vaginal secretion pH testing using pH paper 4-6.
  - Saline "wet mount" for microscopic examination (performed by licensed clinician or laboratory staff certified or trained to read vaginal wet mounts):
    - Document the presence of and percentage of cells that are "clue cells."

- If motile flagellated protozoa are seen, the subject will be excluded from participating in the trial and referred to her provider to be treated using established standards.
- KOH 10% "wet mount" for microscopic examination (performed by licensed clinician or laboratory staff certified or trained to read vaginal KOH preparations):
  - Document presence or absence of fishy odor on "whiff test": fishy (amine) odor released by the addition of a drop of 10% KOH to the vaginal discharge.
  - Document presence of pseudohyphae or budding spores.

The subject will be enrolled based on demonstration of any three of the four following Amsel criteria:

- Off-white (milky or gray), thin, homogenous discharge with minimal or absent pruritus or inflammation of the vulva or vagina.
- ≥20% "Clue" cells of total epithelial cells on microscopic examination of saline wet mount.
- Vaginal secretion pH >4.5.
- Positive "whiff test".

\*\*\*If the subject does not meet clinical criteria (based on Amsel criteria) for BV, she will not have further vaginal sampling performed and will not proceed to randomization and will not receive study drug.

#### If subject demonstrates evidence of BV:

For those subjects who have evidence of BV based on the above criteria and continue to meet inclusion/exclusion criteria, samples will be collected in the following order:

- Vaginal swabs for the following:
  - Gram stain of vaginal smear (local laboratory preparation and shipment to the University of Iowa Clinical Pathology Laboratory).
  - Culture or molecular testing for the following will be taken:
    - OSOM® rapid Trichomonas testing. OSOM testing is required if the
      wet prep shows no evidence of motile flagellated protozoa. If the wet
      prep was positive for motile protozoa, then the diagnosis of trichomonas
      has already been confirmed and OSOM testing is not required. If
      positive for Trichomonas, the subject will be excluded from
      participating in the trial and referred to her provider to be treated using
      established standards
    - Bacteria and Candida species (to be sent to the Central Laboratory).
    - Chlamydia trachomatis testing should be performed as per local standards (to be sent to the Local Clinical Pathology Laboratory). If study subject has had Chlamydia trachomatis testing performed within the past 5 days

- and it was negative or is still pending, this data may be used for screening. Vaginal swab testing is the preferred method for testing in this study, but if urine testing has been done within the past 5 days, this is acceptable. If Chlamydia testing is positive, the subject will be contacted by telephone and letter and referred to her provider for further management.
- Neisseria gonorrhoeae testing should be performed as per local standards (to be sent to the Local Clinical Pathology Laboratory). If study subject has had Neisseria gonorrhoeae testing performed within the past 5 days and it was negative or is still pending, this data may be used for screening. Vaginal swab testing is the preferred method for testing in this study, but if urine testing has been done within the past 5 days, this is acceptable. If gonorrhea testing is positive, the subject will be contacted by telephone and letter and referred to her provider for further management.
- Future Use: If the subject consents to future use, one Copan ESwab in liquid amies will be collected for future use (to be transported on cold packs or ice to the research laboratory).
- Obtain approximately 15 cc of blood to be sent to the local Clinical Pathology Laboratory for WBC count, hemoglobin, platelet, neutrophil count, creatinine, AST, ALT, total bilirubin, random glucose, and HIV testing. If HIV testing has been performed within the past 5 days and was negative or is still pending, this test can be used for screening.
- Once all samples have been obtained, the subject will be enrolled in IDES and randomly assigned to a treatment group.
- Subjects will be counseled on proper administration and storage of the vaginal gel.
- Subjects will self-administer the first dose of the investigational vaginal gel or vehicle placebo gel with observation by study personnel while in the clinic using the first applicator in the assigned study kit.
- Subjects will receive 5 further doses (vaginal applicators with instructions) for self-administration twice-daily (morning and evening) with at least 8 hours between doses.
- Subjects will be instructed to return used applicators to the disposal bag provided in the kit to return to the clinic at Visit 2 (between Study Days 8-15).
- Review for AEs/SAEs
- Provide counseling to refrain from penile-vaginal or receptive oral sexual intercourse or insertion of any substance (other than study product), products, or objects between Visit 1 and Visit 2 and 48 hours prior to Visit 3.
- Provide memory aid and instruct subject on how to complete the memory aid for 5 days from the first day of therapy.
- Counsel subjects on avoidance of pregnancy (for all female subjects of childbearing potential).

\*If a subject's laboratory results show a positive gonorrhea, chlamydia, HIV test or grade 3 abnormality, study personnel will contact the subject to inform her of the results and instruct

her to discontinue study treatment. Telephone contact is the preferred method of contact, though initial contacts may include other forms of communication with follow-up discussions provided by telephone or in person.

